5.3.2. Study Termination

The Data Monitoring Board and Sponsor have the right to discontinue a site or terminate the trial for the following reasons:

- The DMB and Sponsor may terminate the study for safety reasons
- A decision on the part of the Sponsor to suspend or discontinue testing, evaluation, or development of the product for any reason
- The Sponsor may decide to close a study site when the Investigator fails to enroll patients into the study at an acceptable rate
- Failure of the Investigator to comply with pertinent regulations of appropriate regulatory authorities
- Insufficient adherence to protocol requirements
- Submission of knowingly false information from the research facility to the Sponsor, Study Monitor, or appropriate regulatory authority

If the study is terminated early, all specified follow-up data on participants enrolled prior to termination will be collected and reported.

6. Study Material & Methods

6.1. Study Device

Investigational devices will be supplied to the research site by DelaRange on behalf of CLJI. The trial devices will be labeled as Investigational Use Only (specific language will vary based on geography). Each device will have a unique product identifier, and this information will be included both in the participant's medical file as well as given to them after the procedure. The Instructions for Use for the VIBLOK cream are provided.

6.2. Storage & Labeling

The VIBLOK cream is to be stored as specified on the unit labels, and in a secure location where only study personnel can access the device for use. The VIBLOK cream will be appropriately labeled to identify their investigational nature.

6.3. Device Accountability

The Investigator shall maintain records of the receipt and disposition of the investigational device. A device disposition log supplied by CLJI to the research site will be used to record devices received from DelaRange, participant hand-out, use, and discards, and devices returned to DelaRange. The participants should return all devices, including emptied packages to research site, and the Investigator shall return to CLJI used and unused devices/ packages, along with the completed device disposition log at completion of the investigation. Use of the VIBLOK cream is prohibited outside of this protocol.

Device disposition will be verified by the clinical monitor periodically throughout the study.

7. Evaluation of Safety

7.1. Definitions

An Adverse Event (AE) is any untoward medical occurrence, unintended disease or injury, or untoward clinical signs (including abnormal laboratory findings) in subjects, users or other persons, whether or not related to the investigational medical device.

A Serious Adverse Event (SAE) is any adverse event that:

- a) leads to death
- b) leads to a serious deterioration in the health of the subject that
 1. results in a life-threatening illness or injury
 2. results in a permanent impairment of a body structure or a body function
 3. requires in-patient hospitalization or prolongation of existing hospitalization
 4. results in medical or surgical intervention to prevent permanent impairment to a body structure or a body function
- c) leads to fetal distress, fetal death, congenital abnormality or birth defect

Adverse Device Effects and Serious Adverse Device Effects are those AEs and SAEs that occur as an untoward or unintended response to a medical device. These events include those which result from insufficiencies or inadequacies in the Instructions for Use or deployment of the device as well as user error.

Unanticipated Serious Adverse Device Effect (USADE) is defined as any serious adverse effect on health or safety or any life-threatening problem or death caused by – or associated with – the device, if that effect, problem or death was not previously identified in nature, severity, or degree of incidence in the investigational plan (including documents such as the protocol, Investigator's Brochure, informed consent form or other study-related documents), or any other unanticipated serious problem associated with the device that relates to the rights, safety or welfare of subjects.

Adverse events may be volunteered by participants, elicited from questioning by Investigator or designee, or collected via observation by the Investigator. In addition, participants will be instructed to contact the investigator, and/or study coordinator if any significant adverse events occur between study evaluation visits.

7.2. Adverse Event Assessments

The Investigator will determine whether or not the event is related to the device and/or procedure, and whether or not the event meets serious criteria. Pre-existing medical conditions or symptoms reported prior to the participant's enrollment will not be recorded as an AE. In the event there is a worsening in the pre-existing medical condition or symptoms then an AE must be recorded.

If it is determined that an AE has occurred, the investigator should obtain all the information required to complete the study AE Form. The causal relation of the event to either the investigational device or to the procedure will be categorized by the Investigator as follows:

None – AE is not associated with the investigational device or procedure.

Remote – AE had minimal or no temporal relationship to the use of the investigational device and/or a more likely alternative etiology exists.

Possible – AE had a strong temporal relationship to the use of the investigational device or procedure and there is no contradicting evidence that can reasonably explain the subject's condition.

Probable or Definite – AE had a strong temporal relationship to the use of the investigational device or procedure and another etiology is highly unlikely.

All AEs will be reviewed by the Study Safety Officer. The AE will be assessed as to its seriousness and relationship to the device, the procedure, and whether it was anticipated or not anticipated.

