8.1.1. Risks/ Adverse Events associated with the disease state

Complications associated with an HSV-2 infected population may include, but are not limited the following:

- Recurrences of genital herpes
- Systemic symptoms, including fever headache, malaise and myalgia's
- Local pain and itching
- Dysuria
- Tender lymphadenopathy

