### 5.2 Adverse Events

#### 5.2.1 Primary endpoint

The primary endpoint of this study is a safety endpoint:

The number of Serious Adverse Device Effects during minimally 26 days of VIBLOK use. A two-sided exact 95% Clopper-Pearson confidence interval will be calculated. The study will be considered a success in case the upper limit of the 95% confidence interval is below 10%.

The analysis will be based on the As Treated Population and repeated for the Per Protocol Population.

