#### 5.2.2 Display of adverse events

All adverse events occurring after initiation of study treatment (including events likely to be related to the underlying disease or likely to represent concomitant illness) will be displayed in summary tables.

The tables will list each adverse event, the number of participants in whom the event occurred, and the rate of occurrence.

Adverse events will be grouped by the following categories:

- Any event
- Bleeding / Anaemia
- Bowel
- Cardiac
- Malignancies
- Miscellaneous
- Neurological
- Pulmonary
- Renal
- Urogenital
- Vascular
- Genital

- Skin
- Infection
- Trauma
- Other

The analysis of adverse events comprises the following categories:

- Any adverse event
- Any adverse event by consideration
- Adverse events considered to be a toxic reaction
- Adverse events considered to be an allergic reaction
- Adverse events considered to be an infection
- Adverse events considered to be other
- Any adverse event by severity
- Possibly, probably or definitely related to investigational device adverse events
- Possibly, probably or definitely related during application of the investigational device adverse events
- Possibly, probably or definitely related after application of the investigational device adverse events
- Possibly, probably or definitely related to study procedure adverse events
- Adverse events related to a pre-existing / other medical condition
- Adverse event related complications associated with an HSV 2 infection
- Any adverse event
- Recurrence of genital herpes
- Systemic symptoms
- Fever
- Headache
- Malaise
- Myalgia(s)
- Local pain and itching
- Dysuria
- Tender lymphadenopathy
- Unanticipated adverse events
- Adverse events by action taken
- No action taken
- Drug Therapy
- Any
- Prescription
- Non-Prescription
- Surgical intervention or other invasive therapy
- Hospitalization
- Other treatment / procedure
- Withdraw from study due to AE
- Adverse events by outcome
- Resolved
- Resolved with sequelae
- Ongoing
- Ongoing at time of exit
- Unknown / Lost to Follow-up

- Death
- Reportable adverse events

Serious adverse events will only be listed as it will be expected that there will only be very few or no serious adverse event.

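### The causality categories in Protocol 7.2 are not exhaustive, so some ambiguous events may be left out of the device-related counts

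*Protocol*

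**What the plan says.** Protocol 7.2 has the investigator place the relation of each event to the device or procedure in one of four categories:

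- None: the event is unconnected with the device and with the procedure.
- Remote applies where "AE had minimal or no temporal relationship to the use of the investigational device and/or a more likely alternative etiology exists".
- Possible: the temporal relationship is strong, and "there is no contradicting evidence that can reasonably explain" the participant's condition.
- Probable or Definite: the temporal relationship is strong, and any other cause is very improbable.

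There is no category for an event that cannot be assessed, and no default. The Study Safety Officer then reviews all events for seriousness and relationship, but no separate criteria are given.

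Protocol 8.5 defines an adverse device effect as an event related to use of the device, and a SADE as such an effect with a serious outcome. Neither document says which of the four categories count as related for the primary endpoint. The only cut-off is in the tables of SAP 5.2.2, which include a row for "Possibly, probably or definitely related to investigational device adverse events". SAP 5.2.1 gives the primary criterion: "The study will be considered a success in case the upper limit of the 95% confidence interval is below 10" per cent.

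Protocol 8.1.1 lists "Local pain and itching" among the events expected from the disease. Protocol 8.1.2 lists toxic or allergic reactions and sensitization as risks of the cream.

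**The concern.** Every treated participant has recurrent HSV-2, and the disease can produce local complaints that look like a reaction to a cream. For such an event the investigator may well see close timing and two explanations of similar weight. The scale has no box for this. Possible is set nearly as high as Probable or Definite, because taken literally it excludes any event that something else can reasonably explain. An investigator who applies it literally has only the lower categories left, and an event placed there does not appear in the related tables.

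The trial is open-label with a single arm, so there is no control group against which a shortfall in related events would show. The related-event tables are part of the safety evidence intended to support the CE mark application, and they should not depend on how each investigator resolves a gap in the definitions.

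**Working it through.** **Step 1: test two events against the four definitions.**

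Case A has strong timing and an HSV-2 explanation that is reasonable but no more likely than the cream. Case B has timing between minimal and strong, with no more likely alternative.

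| Category | Case A | Case B |
|---|---|---|
| None | Not met: an association has not been ruled out | Not met: same reason |
| Remote | Not met: timing is strong, and the alternative is not more likely | Not met: timing is more than minimal, and no alternative is more likely |
| Possible | Timing met; fails because HSV-2 can reasonably explain the event | Not met: timing is not strong |
| Probable or Definite | Timing met; fails because the alternative is not very improbable | Not met: timing is not strong |

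Neither case has a category. The gap in Case A lies between "a more likely alternative etiology exists" in Remote and "there is no contradicting evidence that can reasonably explain" in Possible: an equally likely cause is too weak for the first and too strong for the second. In Case B it lies between "AE had minimal or no temporal relationship to the use of the investigational device" and the strong relationship that the two higher categories require. Case B is limited by the and/or in Remote: intermediate timing with a more likely alternative is properly Remote.

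**Step 2: follow the event into the analysis.** SAP 5.2.2 counts possible, probable and definite as related. A Case A or B event put in Remote or None is absent from those rows; one put in Possible is present. These tables are descriptive: SAP 1.3 tests no hypothesis on adverse events. The documents give no frequency of ambiguous events, so the size of this effect cannot be calculated.

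**Step 3: reproduce the primary-endpoint figure.** The inputs are n = 36, a two-sided exact 95% interval and a 10% limit (Protocol 9.1, SAP 1.4 and 5.2.1). The Clopper-Pearson upper limit is the 0.975 quantile of Beta(x + 1, n − x). For x = 0 this equals 1 − 0.025^(1/n).

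- n = 35: 10.00%, not below 10%.
- n = 36: 9.74%, below 10%. The plan's 36 is reproduced, on the basis of zero events.

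**Step 4: zero against one SADE at the planned sizes.**

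| n | Upper limit, 0 SADE | Upper limit, 1 SADE |
|---|---|---|
| 36 | 9.74% | 14.53% |
| 42 | 8.41% | 12.57% |
| 46 | 7.71% | 11.53% |

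At these sizes the criterion is met only with zero SADEs. With one SADE the limit is 10.07% at n = 53 and 9.89% at n = 54, so at least 54 participants would be needed.

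**Step 5: how often a SADE is expected.** At the planned incidence of 0.1%, the chance of at least one participant with a SADE among 46 is 1 − 0.999^46 = 1 − 0.955 = 4.5%. The event would also have to fall in the gap for this point to matter to the primary result.

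**The case against.** The strongest reply is that the practical reach is small, and most of that reply stands.

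- **Serious events.** A reader might infer from Step 4 that the gap puts the primary conclusion at risk. The documents do not support that. A SADE must meet the SAE criteria of Protocol 7.1, such as death, hospitalization or permanent impairment, whereas the natural examples here are local and non-serious. SAP 5.2.2 expects few or no serious events. That one event reverses the result is a property of the success rule, and holds for any error about one serious event.
- **Direction.** A reader might also infer that under-counting is certain. A gap event fails Remote just as it fails Possible, and an investigator may round up. The literal bar in Possible makes rounding down plausible, but no more than that.
- **Reading of Possible.** Being HSV-2 positive is true of everyone and need not be contradicting evidence about one event. Protocol 5.2.6 also provides a lesion swab and an examination for a suspected recurrence. This narrows Case A. It does not remove it where the clinical picture stays evenly balanced, and an equally likely cause is most naturally read as one that can reasonably explain the event.
- **Timing.** With daily application for at least 26 days, most events have close timing, so Case B is uncommon. Classification then rests mainly on the alternative-cause clause, which is where Case A arises.
- **Safeguards.** The Safety Officer reviews every event and the DMC reviews all safety data. SAEs are reported whatever their cause. SAP 5.2.2 and 5.2.3 tabulate and list all events, with causality ratings and separate rows for allergic and toxic reactions. A misplaced event would remain visible. None of these steps supplies a rule for placing it or says whose rating counts.
- **AE form.** It may carry rating guidance. It is not among the documents, so this cannot be checked.

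**Conclusion.** The point holds as a defect in a stated rule. On the plain wording of Protocol 7.2, an event with strong timing and an equally likely alternative has no category, and neither, less often, does one with intermediate timing and no more likely alternative. Nothing elsewhere in the protocol or SAP supplies a default. A related gap is that no relatedness cut-off for SADE is written down; the link to possible or higher is inferred from the table rows in SAP 5.2.2.

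The likely consequence is some loss of events from the descriptive device-related tables, of unknown size. The primary endpoint is affected only if an ambiguous event is also serious, which the plan's own assumption makes rare.

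The conclusion assumes that an equally likely HSV-2 cause counts as a reasonable explanation, and that the AE form adds no guidance that closes the gap.

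**What to change.** In Protocol 7.2 and the AE form, redefine Possible as a plausible temporal relationship to the device or procedure, with an alternative cause that is equally or less likely or cannot be excluded. Keep Remote for events with a more likely alternative or implausible timing. The categories are then exhaustive, and Probable or Definite can stay as it is.

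In SAP 5.2.1, state that an SAE rated possible or higher counts as a SADE, so that the primary endpoint uses the same cut-off as the tables in SAP 5.2.2. Whether a rating by the investigator or by the Safety Officer prevails is a separate choice about adjudication, which this change does not require.

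The cost is wording in the protocol, AE form and SAP. Sample size, treatment and visits do not change. The downside is that a few more events may be counted as device-related, so the safety figures may look slightly less favourable.

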7.3. Device Deficiency

Device deficiency is an inadequacy of a medical device with respect to its integrity, quality, durability, reliability, safety or performance. It includes malfunctions, user errors and inadequate labeling.

Device deficiencies that did not lead to an adverse event but could have led to a medical occurrence:

- a) If either suitable action had not been taken,
- b) If intervention had not been made, or
- c) If circumstances had been less fortunate.

Reporting conventions for device deficiencies that could result in an SAE are the same as those for an actual SAE.

7.4. Adverse Event Reporting

AEs are reported beginning from enrollment until participant participation has ended (i.e. completion of study or withdrawal of consent). Adverse events must be followed until resolution, AE has stabilized, or the study has been completed.

All Serious Adverse Events (SAE) must be reported to CLJI Worldwide within 24 hours of the Investigator becoming aware of the event or according to local regulations (whatever is more stringent). Information may be entered into the electronic adverse event form or reported directly to the Safety Officer of CEPARTNER4U:

[name]

[contact]

[contact]

[contact]

e-mail: [contact]

At the time of initial notification, the following minimal information must be provided:

- Identifiable participant: participant number
- Identifiable reporter: study site
- Adverse event description
- Causal relationship to device and procedure
- Awareness date

The site will provide to CLJI Worldwide (or designee) a copy of anonymized supporting documentation (such as hospital record, laboratory results, autopsy results) of all SAEs.

SAEs will be reported to the ethics committee (EC) and regulatory authorities as required by national regulations or by the EC itself.

All SADEs must be reported to CLJI Worldwide within 24 hours of the Investigator becoming aware of the event or according to local regulations (whatever is more stringent). The AE Forms of the CRF must be completed with 5 working days for all SADEs. The Investigator is also responsible for notifying his/her EC of all SADEs occurring at his/her site (and any additional information as required by EC or local regulations). All SADEs must be followed until resolution or until a stable clinical endpoint is reached. All required treatments and outcomes of the SADE must be recorded.

CLJI will notify all participating clinical Investigators, ECs, and competent authorities as necessary of all SADEs that occur during this study within with the specified reporting time after he/she first receives notice of the effect. Investigators are responsible for reviewing information received about SADEs.

Device deficiencies which could have led to a serious adverse device effect should undergo the same reporting as serious adverse events, i.e., they should be reported to CLJI Worldwide within 24 hours of awareness; and to the ethics committee and regulatory authorities as required by national regulations or by the ethics committee.

8. Risk Evaluation

8.1. Potential Risks to Study Participants

For purposes of this study, adverse events that may be anticipated are associated with the use of VIBLOK cream as well as the procedures used to deploy the cream.

Anticipated risks have been minimized to the furthest extent possible (full details of the risk management procedures can be found in the CIB), but the nature of the patient's disease state has inherent risks [22].

8.1.1. Risks/ Adverse Events associated with the disease state

Complications associated with an HSV-2 infected population may include, but are not limited the following:

- Recurrences of genital herpes
- Systemic symptoms, including fever headache, malaise and myalgia's
- Local pain and itching
- Dysuria
- Tender lymphadenopathy

8.1.2. Risks/ Adverse Events associated with VIBLOK cream

In addition to the events listed in the previous section, the additional adverse events listed below are specifically associated with the VIBLOK cream and its application. The lack of data associated with long term VIBLOK usage prevents predicting the incidence of these risks. Additional complications include, but may not be limited to:

- Toxic, hypersensitive or allergic reaction

- Epithelial sensitization

8.1.3. Risks associated with study procedures

Study procedures may impose additional risks to study participants. In case of the SAFE Trial this theoretically could concern an increased risk for HSV infection of

- housemates, or
- other places than the extra-genital region

due to the frequent sampling and/ or touching of the extra-genital area.

HSV is transmitted via direct contact with infected secretions, such as during sexual intercourse. Casual contact, sharing of bathroom, toilet seats, etc. have not been implicated in HSV transmission. Furthermore, sampling and cream application is only done when participants are asymptomatic, which in principle is not different from normal hygienic or sexual behavior. Therefore, swabbing of the genital area by a study participant does not pose a risk to housemates.

The likelihood of spreading the virus to another part of the body is nil, since autoinoculation does not occur in persons who are infected outside of the primary episode as then immunity has been established. Of note, in that respect is that the University of Washington HSV research group has been using self-collected swabs for study of HSV for >25 years, and neither autoinoculation, nor exposure of housemates has ever been suspected as a result of these procedures.

In summary, the likelihood for imposing additional risks to study participants and their housemates due study procedures is considered negligible.

8.2. Methods to Minimize Risk

Product handling and procedure guidance are provided in the Training Materials, and will be used for device training to minimize risks associated with device use.

Additionally, efforts will be made to minimize and/ or early capture of these possible risks through site/investigator selection and management. Site and investigator selection criteria are established to ensure that the study personnel and their institutions are qualified to screen, perform and manage the study procedures as well as support the associated requirements for research. Also trial management structure is designed to provide disciplined oversight of the trial activities including monitoring of site and personnel performance.

Site and investigator criteria include the following:

- Investigational site personnel must be experienced and skilled in treating participants with viral STI's.
- Good collaboration with general practitioners to ensure proper participant follow-up.
- The study site must have an adequately staffed research department with a minimum of one dedicated study coordinator.
- Able to enroll a minimum of 5 participants

Although the risk associated with the study procedures is considered negligible as compared to normal practice, the study participants will be instructed to wash their hands thoroughly after their (daily) sampling.

